
Despite thrombolytic therapy, angioplasty (PCI) and progress in recent decades have significantly improved the prognosis of patients after a heart attack with or without increase in the ST tract, the overall mortality rate is 8% to one month and 12% a year after discharge [3]. It has also been estimated that, following a myocardial infarction, about 40% of STEMI patients and 30% of NSTEMI patients develop a remodelling of the left ventricle (VS) resulting in contractile dysfunction within 12 months [4, 5].

Previous studies Randomized clinicians identified a left ventricle ejection fraction (FEVS) < 45 as cut-off to define a left ventricular systolic dysfunction [6]. The development of a Left ventricular dysfunction is one of the largest independent predictors of mortality after heart attack myocardial [3, 7]. In contrast to patients with acute myocardial infarction, patients with AU, have a preserved FEVS (>60%), an excellent prognosis and a low rate of evolution towards ventricular dysfunction at one year (5-7%) [8]. The AU, characterized by ischemia in the absence of cardiomyocytic necrosis, with the advent of high sensitivity tests for the dosage of troponins thistle accounts for 10% of all ACS [8].

Many circulating proteins, such as Creatine Kinase (CK-MB), cardiac troponin measured with high sensitivity test (hs-cTn), type B Natriuretic Peptide (NT-proBNP), the binding protein fatty acids (H-FABP), lactate dehydrogenase (LDH) have been studied for their potential as biomarkers and used (hs-ctn and NT-proBNP) in the diagnosis and prognosis of dysfunction ventricular [7]. LV pathological remodeling is characterized at the molecular level by a alteration of the expression of different transcripts be they encoding (mRNA) or non-coding (ncRNA) [9, 10]. In particular, circulating RNA, present both in the plasma and within the cells blood, is highly stable and easily measurable even if present at very low concentrations.

In addition, the potential of circulating RNA for use as biomarkers has been known for some time cardiovascular [11-13].

Objective of the project

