We propose to carry out an observational, prospective study that involves the evaluation of predictive circulating biomarkers of ventricular dysfunction (FE <45%) in patients with ACS. In particular our aim will be to check if there are transcripts circulating in the blood peripheral, coding or not for proteins (mRNAs or ncRNAs), differently modulated in patients with ACS (ACS_signature) submitted to PCI, distinguished on the basis of the evolution towards dysfunction ventricular. Our study will be based on transcriptomic analysis of the entire genome.

Objectives

Primary objective:

Detect circulating transcripts encoding proteins (mRNAs) or not (ncRNAs) (ACS_signature) predictive ventricular dysfunction in patients with ACS undergoing PCI.

Secondary objective:

Evaluate the association of the ACS_signature with possible adverse events at 12 months and its prognostic ability in the prediction of adverse events additional to the use of standard clinical parameters. Adverse events are defined: death from cardiovascular causes, re infarction, non-fatal stroke, new coronary revascularization, arrhythmias, development of heart failure and new hospitalizations for cardiovascular causes.

Study population

378 patients with a first episode of ACS (STEMI, NSTEMI and UA) will be recruited to PCI.

Criteria for Inclusion:

1. Age >18 years
2. ACS patients (first episode), defined according to ESC 2017 guidelines [14]
3. Indication for treatment of percutaneous revascularization
4. Informed consent to enrol in the study

Exclusion Criteria

1. Severe valvulopathy or other conditions requiring cardiac surgery
2. Previous cardiac surgeries including coronary bypass
3. Total chronic occlusion
4. Patients with known hypersensitivity or contraindication to one of the following drugs:
 - heparin
 - aspirin,

- clopidogrel,
 - ticlopidine,
 - sirolimus,
 - everolimus.
5. Any contraindication to medicated stent implantation (DES)
 6. Patients with previous documented myocardial infarction;
 7. FEVS <30% before PCI
 8. Patients in cardiogenic shock
 9. Patients with evolved STEMI (> 48 h from onset of symptoms/Q-waves to ECG) or undergoing to fibrinolysis
 10. Patients with known previous cardiomyopathy with FEVS < 40%
 11. Patients with malignant neoplasm or systemic disease with a "quoad vitam" prognosis less than 1 year
 12. Patients with known active infectious diseases;
 13. Patients who are unable to give valid informed consent at the time enlistment

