 14. Pregnant women

Study design

This study, observational, prospective, monocentric will rely on the recruitment of patients consecutive with acute coronary syndrome (STEMI, NSTEMI) treated with angioplasty. I am 4 years and 6 months for recruitment and 12 months thereafter for completion of the follow-up, followed by a period of three months to complete the data analysis. Recruitment will be divided into two phases, functional to the subsequent molecular analysis: one of discovery and one of validation, partially overlapped temporally. Based on literature and experience data previous [5], we expect the number of patients who will develop ventricular dysfunction at 12 months from the PCI will be higher among the STEMI than the NSTEMI. A number of NSTEMI patients higher, so the number of patients who will develop ventricular dysfunction will be similar between these two groups. In addition, 100 patients diagnosed with AU, in which a low rate of evolution towards left ventricular dysfunction, will form a group of further control that will be tested after the validation phase, more relevant and homogeneous compared to healthy patients.

	MONTHS																																								
	1	2	3	4	5	6	7	8	9	10	11	12	13	14	15	16	17	18	19	20	21	22	23	24	25	26	27	28	29	30	31	32	33								

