3.2. EXP ACTIVITY VALIDATION: VALIDATED ACS_SIGNATURE																																									
3.3. CODE BROKEN, CORRELATIONS AND STAT ANALYSIS																																									

Assessments	Pre-procedure	Post-procedure (12-24 h)	6 months	12 months
Medical History*	X		X	X
Recruitment criteria	X			
Blood draw ACS_SIGNATURE	X	X	X	X
Blood count*	X	X	X	X
Blood draw Tn-hs e CK-MB*	X	X		
ECG*	X	X	X	X
Echocardiography *	X	X	X	X
Angiography *	X			
Endpoints			X	X

* routine clinical evaluations

Patients will be enrolled after diagnosis of ACS and before coronary surgery and will be treated according to the guidelines provided for the treatment of acute coronary syndrome and for post-PCI. Unless special contraindications, all patients will receive optimal medical therapy that includes:

- Dual therapy for 12 months
- Statins
- beta-blockers,
- ACE inhibitors,
- Mineralocorticoid receptor antagonists.

Follow-up visits including echocardiographic examination will be performed at 6 and 12 months from myocardial revascularization procedure. The evaluation of the FEVS will be carried out by 3D echocardiography that, as has been documented, shows a proven concordance with the MRI [15]. This method has also shown high reproducibility, with low intra- and inter-operator variability, and increased diagnostic accuracy. During the echocardiographic examination, in addition to FEVS data, other function indices will be evaluated systolic left ventricle such as, for example, telesistolic volumes, telediastolic, parameters tissue Doppler derivatives and myocardial strain indices (global Longitudinal strain).

The study will also need to take samples that will be made with the following scheme: 1) pre operative, before PCI, 2) post-operative 1 taken at 12 - 24h from PCI, 3) post-operative2 -6 months after PCI and 4) post-operative3-12 months after PCI.

Pre-operative withdrawal will be performed in the recovery room of the hemodynamics room after diagnosis of ACS. The post-operative withdrawal.1 will be performed at the Department of Cardiology 12/24 hours after the procedure. Post-operative.2 and post-operative.3 withdrawals will be performed outpatient during the planned echocardiographic checks (6 and 12 months respectively).

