RNA that will pass validation (Validated ACS_Signature), will be further tested also in the AU control group and all other timepoints, to assess the time trend potential biomarkers. In addition, the expression of the Validated ACS-Signature will be evaluated in the plasma and whole blood, to assess biodistribution and translational potential. Patient recruitment, withdrawals, patient data collection and all clinical procedures requests will be made by the Clinical, Interventional and Intensive Care Cardiology Unit Coronary Surgery (UTIC) of the IRCCS Policlinico San Donato. The collection and conservation of blood and pre-analytic treatment will be carried out at the BioCor Biobank of the IRCCSPoliclinico San Donato, while RNA measurements will be carried out in the Laboratory of Molecular Cardiology of IRCCS Policlinico San Donato. The study of modulated transcripts by RNA Sequencing with library preparation, sequencing and analysis bioinformatics will be carried out at the Center for Translational Genomics and bioinformatics, of the San Raffaele Hospital.

Sample size

Based on literature [4, 5] it is expected that about 40% of STEMI patients and 30% of STEMI patients NSTEMI patients, after a first episode of myocardial infarction, experience dysfunction of the left ventricle.

Based on these data, we expect recruiting in 18 months 278 patients with ACS performing PCI, 100 will experience ventricular dysfunction (Table 1).

Table 1. Patient recruitment and follow up				
Study phase	Total number of patients		Dysfunction LV expected	
	STEMI	NSTEMI	STEMI	NSTEMI
DISCOVERY	49	75	20	22
VALIDATION	61	93	31	28
TOTAL STEMI + NSTEMI	110	168	50	50

The number of patients to be recruited will be 378, of which 110 STEMI, 168 NSTEMI and 100 AU, as control. By preventing 100 events in total, respectively 50 per group, you can enter about 6/7 variables for each model of multivariate logistic regression (STEMI NSTEMI). Experimental RNA measurement activities shall follow the distribution shown in Table 2.

Table 2. Experimental activity				
	DISCOVERY		VALIDATION	
	STEMI	NSTEMI	STEMI	NSTEMI
LV DYSFUNCTION	20	20	50	50
NO LV DYSFUNCTION	20	20	60	118
TOTAL	40	40	110	168

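### Tables 1 and 2 allow for no loss before a classifying echo; separately, and with larger effect, the STEMI event total of 50 is not what the protocol's own 40% gives (44)

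*Protocol*

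**What the plan says.** The Sample size section applies dysfunction rates of about 40% (STEMI) and 30% (NSTEMI) and concludes: "we expect recruiting in 18 months 278 patients with ACS performing PCI, 100 will experience ventricular dysfunction". Table 1 gives the following.

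| | STEMI patients | STEMI events | NSTEMI patients | NSTEMI events |
|---|---|---|---|---|
| Discovery | 49 | 20 | 75 | 22 |
| Validation | 61 | 31 | 93 | 28 |
| Total | 110 | 50 | 168 | 50 |

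Table 2 then sets the validation work at 50 with and 60 without dysfunction (STEMI), and 50 with and 118 without (NSTEMI). Its discovery work has 20 patients in each of four cells. Model size follows from the event count: "By preventing 100 events in total, respectively 50 per group, you can enter about 6/7 variables for each model of multivariate logistic regression".

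The Study design section refers to "the number of patients who will develop ventricular dysfunction at 12 months from the PCI". The echo schedule is: "Follow-up visits including echocardiographic examination will be performed at 6 and 12 months from myocardial revascularization procedure". On prognosis, the Introduction says that "the overall mortality rate is 8% to one month and 12% a year after discharge", and describes remodelling "resulting in contractile dysfunction within 12 months". The exclusion criteria remove "Patients in cardiogenic shock" and "FEVS <30% before PCI".

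**The concern.** A patient can be placed in either row of Table 2 only if a follow-up echo exists. Table 2 places every recruit, so the event counts, the variables per model and the discovery cells all assume that nobody dies or misses the echo. The protocol states these figures itself, so they are not details left to a later plan.

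The STEMI events also do not follow from the stated rate, even with complete follow-up. Two separate effects therefore push the same way. What is at stake is how many variables each logistic model can carry and whether the discovery cells can be filled as drawn. The Statistical methods section wants the signature assessed against NT-proBNP, Tn-hs and CK-MB, so one or two fewer variables is a practical limit.

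**Working it through.** **Inputs.** 110 STEMI and 168 NSTEMI; rates 40% and 30%; discovery recruits 49 and 75; 50 events for 6/7 variables; validation SD 1.4 and alpha 0.01 with a 2.2-fold difference (all from Sample size). The mortality figure of 12% is from the Introduction. The protocol gives no loss rate for this cohort. I assume L = 5% to 12%, where loss means no echo that classifies the patient.

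**1. Is zero loss built in?** 50 + 60 = 110 and 50 + 118 = 168. Classified equals recruited, so yes.

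**2. Reproducing the stated events at zero loss (N × rate).**
- Discovery STEMI: 49 × 0.40 = 19.6 (stated 20). Agrees.
- Discovery NSTEMI: 75 × 0.30 = 22.5 (stated 22). Agrees.
- Validation NSTEMI: 93 × 0.30 = 27.9 (stated 28). Agrees.
- Validation STEMI: 61 × 0.40 = 24.4 (stated 31). Does not agree; 31/61 = 51%.
- STEMI total: 110 × 0.40 = 44.0 (stated 50). Does not agree; the column itself sums to 20 + 31 = 51.
- NSTEMI total: 168 × 0.30 = 50.4 (stated 50). Agrees.
- Overall: 44.0 + 50.4 = 94.4 (stated 100).

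Loss can only lower an expected count, so no loss assumption explains the 50.

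**3. Adding loss: N × (1 − L) × rate.** This is the worst case, because it takes the full loss off the events.

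| Loss | Evaluable | STEMI events | NSTEMI events | Total |
|---|---|---|---|---|
| 0% | 278 | 44.0 | 50.4 | 94.4 |
| 5% | 264 | 41.8 | 47.9 | 89.7 |
| 12% | 245 | 38.7 | 44.4 | 83.1 |

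The STEMI shortfall from 50 splits into 50 − 44 = 6.0 events from the arithmetic, plus 44 − 41.8 = 2.2 (5%) or 44 − 38.7 = 5.3 (12%) from loss.

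**4. Variables per model.** The protocol's ratio is 50/7 = 7.14 to 50/6 = 8.33 events per variable. Dividing the events by 8.33 and by 7.14 gives:

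| Loss | STEMI | NSTEMI | Loss alone, on the stated 50 |
|---|---|---|---|
| 0% | 5.3–6.2 | 6.0–7.1 | 6–7 |
| 5% | 5.0–5.9 | 5.7–6.7 | 5.7–6.7 (47.5 events) |
| 12% | 4.6–5.4 | 5.3–6.2 | 5.3–6.2 (44 events) |

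**5. Discovery cells: P(X ≥ 20), with X binomial.** STEMI has n = 49, p = 0.40(1 − L). NSTEMI has n = 75, p = 0.30(1 − L).

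| Loss | STEMI expected | STEMI P(≥20) | NSTEMI expected | NSTEMI P(≥20) | Both cells |
|---|---|---|---|---|---|
| 0% | 19.6 | 51% | 22.5 | 77% | 39% |
| 5% | 18.6 | 39% | 21.4 | 68% | 27% |
| 12% | 17.2 | 25% | 19.8 | 52% | 13% |

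The no-dysfunction cells are not at risk: 49 − 19.6 = 29.4 and 75 − 22.5 = 52.5 are available for 20 places each.

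**6. Validation power.** I take the 2.2-fold difference on the log2 scale, log2(2.2) = 1.14, with SD 1.4 and alpha 0.01 in a t test. At 50 v 50 this gives 95.3% one-sided, which matches the stated 95%, and 92.2% two-sided. The protocol does not state sidedness. For STEMI at the corrected counts (44 v 66, reduced by loss), power at 0 / 5 / 12% loss is 96 / 95 / 94% one-sided or 94 / 92 / 90% two-sided.

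**The case against.** **Loss alone is the smaller effect.** At 5% it leaves 47.5 of the stated 50 events, or 5.7–6.7 variables, which still rounds to the protocol's approximate 6/7. Only the top of the range moves the figure visibly. This stands, and it is why the two effects should be reported apart. The STEMI discovery cell's 51% at zero loss is likewise not a loss effect.

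**The 12% is high for this cohort.** Shock and very low ejection fraction before PCI are excluded, so it is an upper figure for deaths. Some patients lost late may be classified by a 6-month echo. That relief is limited if the 12% is mortality: 8 of the 12 points fall in the first month, so at most 4 could come after a 6-month echo. How such patients are classified may be left to the analysis plan, and I raise no finding on it.

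**Deaths may not lower the events.** If the 40% and 30% already count patients who die in their denominators, deaths reduce only the no-dysfunction cells (stated as 60 and 118). The protocol does not settle this. It stands as a limit on step 3, but Table 2 would still count unclassified patients as free of dysfunction.

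**Three stronger readings are tempting, and the protocol does not support them.**
- A reader might infer that the study is underpowered or must recruit more. Step 6 shows only modest changes in validation power.
- A reader might infer that discovery power fails because a cell is likely to fall short. The 40 patients, 20 per group, may be a pooled size, and then about 17 + 20 cases (17.2 + 19.8 expected at 12% loss) still exceed 20.
- A reader might infer the reverse, that discovery power is safe. But 20 v 20 also matches each discovery column of Table 2. If the size is per stratum, a short STEMI cell falls below the number on which the 94% rests. Neither conclusion can be drawn until the protocol says which is meant.

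**Conclusion.** The point holds as two separate corrections, of moderate weight.

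First, and certain: the STEMI total is wrong as written. The protocol's own rate gives 44, the stated cells sum to 51, and the expected total is 94 rather than 100. The STEMI model then holds about 5 to 6 variables before any loss.

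Second: zero loss is built into both tables. At an assumed 5% to 12% loss, events fall at worst to 41.8–38.7 (STEMI) and 47.9–44.4 (NSTEMI). That leaves about 5 variables in the STEMI model and about 6 in the NSTEMI model. The size of this effect rests on the assumed range and on loss reducing events in proportion.

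The STEMI discovery cell has no margin: a 51% chance of reaching 20 at zero loss, and 25% at 12%. Validation power is little affected. The effect of a short cell on discovery power is open, because the protocol does not say whether the 20 per group is pooled or per stratum.

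**What to change.** With enrolment unchanged:

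1. Correct the STEMI column of Table 1 (44 in total, validation cell about 24), the matching Table 2 split (44 and 66) and the overall total (94).
2. State an assumed loss, for example 5% and 12%. Restate evaluable patients, events and variables per model in Tables 1 and 2 at that loss, after the correction in step 1, so that the two effects can be seen separately.
3. Give the model sizes that follow: about 5 variables for STEMI and about 6 for NSTEMI.
4. Show the discovery cells as expected, not guaranteed, numbers.
5. Say whether the 40 patients (20 per group) in the discovery calculation are pooled or per stratum. If per stratum, restate the 94% power for a cell that falls short.

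The cost is text and table edits only, with no added patients, visits or assays. The downside is slightly less favourable stated figures and a STEMI model smaller by one or two variables.

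### Expected STEMI events in Table 1 do not follow from the plan's own 40% rate: 44 rather than 50, so 94 rather than 100 overall

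*Protocol*

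**What the plan says.** All figures are in the Protocol, Sample size, unless noted.

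- Rates: "it is expected that about 40% of STEMI patients", with 30% for NSTEMI. The wording there is garbled, but the Introduction gives the same two rates clearly.
- Result: the section says that, on the basis of these data, of 278 patients "100 will experience ventricular dysfunction (Table 1").
- Table 1 columns are STEMI n, NSTEMI n, expected STEMI cases and expected NSTEMI cases. The discovery row is 49, 75, 20, 22. The other two rows are "VALIDATION 61 93 31 28" and "TOTAL STEMI + NSTEMI 110 168 50 50".
- Use of the count for model size: "By preventing 100 events in total, respectively 50 per group, you can enter about 6/7 variables for each model of multivariate logistic regression". I read the first verb as anticipating.
- Table 2, last two columns (validation STEMI and NSTEMI): "LV DYSFUNCTION 20 20 50 50" and "NO LV DYSFUNCTION 20 20 60 118".
- Study design explains that more NSTEMI patients are recruited, "so the number of patients who will develop ventricular dysfunction will be similar between these two groups".

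**The concern.** The plan presents its event counts as a consequence of two stated rates, but one cell of Table 1 cannot come from them, and its column does not add to its own total. The resulting 50 STEMI events then determine how many variables the STEMI logistic model may hold and how Table 2 splits the validation samples. A reader cannot tell whether the STEMI assumption is 40% (the text and the discovery row), 45.5% (the total row) or 51% (the validation row). If 40% is meant, the STEMI model is planned on events that the study does not expect to see.

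**Working it through.** **Inputs.** Rates 0.40 (STEMI) and 0.30 (NSTEMI); patient numbers from Table 1. Expected cases = n × rate.

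| Cell | n × rate | Expected | Printed | Implied rate |
|---|---|---|---|---|
| Discovery STEMI | 49 × 0.40 | 19.6 | 20 | 40.8% |
| Discovery NSTEMI | 75 × 0.30 | 22.5 | 22 | 29.3% |
| Validation STEMI | 61 × 0.40 | 24.4 | **31** | **50.8%** |
| Validation NSTEMI | 93 × 0.30 | 27.9 | 28 | 30.1% |
| Total STEMI | 110 × 0.40 | 44.0 | **50** | **45.5%** |
| Total NSTEMI | 168 × 0.30 | 50.4 | 50 | 29.8% |
| Overall | 44.0 + 50.4 | 94.4 | **100** | |

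The method reproduces the plan's discovery STEMI cell and every NSTEMI figure. It fails only for the validation STEMI cell and the totals that depend on it.

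**Addition, with no assumption about rates.** STEMI: 20 + 31 = 51, printed 50. All four cells: 20 + 22 + 31 + 28 = 101, stated 100.

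**Could one other STEMI rate explain the column?** Allowing for rounding to a whole patient:

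- 20 of 49 needs 39.8–41.8% (19.5/49 to 20.5/49).
- 31 of 61 needs 50.0–51.6% (30.5/61 to 31.5/61).
- 50 of 110 needs 45.0–45.9% (49.5/110 to 50.5/110).

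These ranges do not overlap, so no single rate fits. Reading 31 as a misprint for 30 would mend the sum, but 30/61 is still 49%.

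**Table 2.** The STEMI validation column prints 50 + 60 = 110. At 40% it is 44 + 66 = 110.

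**Model size.** The plan's 6/7 variables on 50 events imply 50/7 = 7.1 to 50/6 = 8.3 events per variable. With 44 events that yardstick allows 44/8.33 = 5.3 to 44/7.14 = 6.2 variables, so about 5–6. The NSTEMI model is unchanged.

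**Chance of reaching the printed counts.** These are binomial, with the two types independent and NSTEMI at 30% throughout. The last column uses the STEMI rate that the totals require, because a correctly planned count is itself missed about half the time.

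| Event count | STEMI 40% | STEMI 45.5% |
|---|---|---|
| At least 50 STEMI | 14% | 54% |
| At least 100 in total | 26% | 54% |
| At least 50 in both types | 8% | 30% |

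**qPCR power.** The plan states 95% with 50 per group, a 2.2-fold difference, α = 0.01 and σ = 1.4. I assume the fold difference is on the log2 scale: d = log2(2.2)/1.4 = 1.1375/1.4 = 0.8125. Two-sample t-test:

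| Groups | Two-sided | One-sided |
|---|---|---|
| 50 v 50 (plan's statement) | 92.2% | 95.3% |
| 50 v 60 (Table 2 as printed) | 94.5% | 96.9% |
| 44 v 66 (stated rate) | 93.8% | 96.4% |

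The plan's 95% is reproduced one-sided. Moving from 50 v 60 to 44 v 66 costs less than one percentage point.

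**The case against.** The arithmetic is hard to dispute; the case against is about weight.

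- **Model size.** Six variables on 44 events is 44/6 = 7.3 per variable, still inside the plan's implied 7.1–8.3. Only the seventh falls outside (44/7 = 6.3). This stands: the loss is at the upper end of the range, and 5–6 overlaps 6/7 at six.
- **Similar event numbers.** Study design promises similar, not equal, numbers, and 44 v 50 can fairly be called similar. This stands. The design aim is not defeated; only the printed equality is unsupported.
- **Probabilities.** The 14%, 26% and 8% mean little alone, since even a correct rate gives only 54%, 54% and 30%. They also treat an approximate 40% as exact. The first point is met by showing both columns; the second is a fair caution.
- **Power.** Validation is run in all STEMI and NSTEMI patients, with the types also analysed separately. Even within STEMI, 44 v 66 has more power than the 50 v 50 on which the plan's statement rests. This stands, and no power loss is claimed.
- **Which figure is wrong.** The documents do not show whether the rate, the patient number or the event count is the mistake. At 40%, 50 STEMI events could also be reached with 50/0.40 = 125 STEMI patients. This stands and is reflected in the fix.

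None of this explains 31 of 61 beside 20 of 49, or a column of 51 printed as 50. The approximate wording of the rate does not stretch from 40% in one row to 51% in the next. A text-extraction fault is also excluded, because the 50 recurs in Table 2 (50 + 60 = 110) and in the sentence on model size.

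**Conclusion.** The concern holds. At the stated rates the plan should show 24 validation STEMI cases, 44 STEMI in total (12% below the printed 50) and 94 overall (6% below 100). The error is certain on the plan's own figures and feeds a stated design limit, so it should be fixed. Its consequence is modest: about one variable fewer in the STEMI model, no change for NSTEMI and no material change in qPCR power. No loss of the stated 94% discovery power is claimed.

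The event counts rest on the 40% and 30% rates as given and on a 12-month outcome for every enrolled patient. The power figures rest on the log2 reading of the fold difference. If the rates are not already per enrolled patient, losses to follow-up would lower the total further: for illustration, 94.4 × 0.95 = 90 at an assumed 5% loss and 94.4 × 0.88 = 83 at an assumed 12%.

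**What to change.** Reconcile the STEMI rate, patient number and event count. If 40% is the intended rate:

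- In Table 1, change validation STEMI cases to 24 and the STEMI total to 44, and keep NSTEMI at 50. Change the overall figure in the text to 94.
- In Table 2, change the STEMI validation column to 44 with and 66 without dysfunction.
- Replace the statement of 50 events per group by 44 STEMI and 50 NSTEMI, and restate the limit as about 5–6 variables for the STEMI model and 6/7 for NSTEMI.

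If 50 STEMI events are intended with 110 patients, state and justify a STEMI rate of about 45% and recompute both STEMI cells so that they add to the total. Either route costs corrections to the tables and the accompanying text, and no extra patients; the first also accepts a slightly less favourable STEMI event count and model size. Keeping both 40% and 50 events would instead need 125 STEMI patients, 15 more than planned.

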For discovery activities using RNA-sequencing, based on literature data [16], we assume a sample size of 40 patients (20 per group) to evaluate the 40 transcripts that differentiate patients with ventricular dysfunction and not ventricular dysfunction, out of a total of 17,500 tests, considering a power of 94.0 %, a value of FDR equal to 0.02. For the activities of validation using qPCR, 95% power is obtained by analyzing 50 samples per group evaluating differences between the averages of 2,2 times, with $\alpha=0,01$ and $\sigma=1,4$.

Statistical methods

The characteristics of patients will be presented with the average, median, standard deviation and range interquartile for continuous and frequency variables and % for nominal and categorical variables. The Shapiro-Wilks will be used to check if distributions are Gaussian. For distributions normal, statistical analysis will be carried out with parametric tests while for non-normal distributions a non-parametric statistical analysis will be carried out. Logistic regression models will be used to assess the association between gene characteristics and clinical outcome. In particular, the power discriminatory (c statistics) will be expressed in terms of area under the curve in a Receiver Operating Characteristics (ROC) analysis. Different cut-off levels will be explored for each of which sensitivity, specificity, negative predictive power and positive predictive power will be evaluated. The added prognostic value of ACS_signature in relation to variables will also be assessed traditional clinics including NTproBNP, Tn-hs and CK-MB using the prediction curve.

Ethical aspects

The study will be conducted according to GCP, local laws and rules of the World Medical Association Declaration of Helsinki.

Publication policy

The data collected are the property of IRCCS Policlinico San Donato and will be the subject of publication.

Bibliography

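### The 6/7-variable allowance counts terms entered, not transcripts searched: if single transcripts are chosen in the same patients, the signature's c-statistic and added value will be overstated

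*Protocol*

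**What the plan says.** Sample size gives the event basis, "By preventing 100 events in total, respectively 50 per group", and concludes that "you can enter about 6/7 variables for each model of multivariate logistic regression (STEMI NSTEMI". The recruits are given as "of which 110 STEMI, 168 NSTEMI and 100 AU, as control". Table 2 splits the qPCR groups into 50 with and 60 without dysfunction (STEMI) and 50 with and 118 without (NSTEMI).

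The discovery calculation in the same section is made "to evaluate the 40 transcripts that differentiate patients with ventricular dysfunction and not ventricular dysfunction, out of a total of 17,500 tests". Its FDR is 0.02 and its power 94%. The qPCR calculation that follows uses 50 per group, a 2.2-fold difference, alpha 0.01 and sigma 1.4.

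Statistical methods specifies logistic regression with a c-statistic. It also plans to assess the signature's added prognostic value against "traditional clinics including NTproBNP, Tn-hs and CK-MB using the prediction curve".

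Study procedures describes the signature as a set of differentially expressed transcripts. It sends them to qPCR in every enrolled STEMI and NSTEMI patient and carries forward those that pass. The Table 2 qPCR totals confirm that discovery patients are included: 110 = 49 + 61 and 168 = 75 + 93, the sums of the discovery and validation rows of Table 1.

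**The concern.** A limit on the number of terms protects against overfitting when the terms are named beforehand. It does not do so when a few terms are picked from a long list by looking at the outcome, because the search itself uses up information. The protocol sets a limit of 6/7, plans around some 40 transcripts, and states no score, reduction rule or shrinkage that connects the two.

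The secondary objective asks whether the signature adds prognostic ability to standard clinical parameters. The comparison is unequal if the clinical markers are fixed in advance while the transcripts are the best few of many in the same patients. The reported c-statistic would then favour the signature for reasons that do not carry over to new patients.

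**Working it through.** **1. The plan's own figure.** 50/6 = 8.3 and 50/7 = 7.1, so 6/7 corresponds to about 7-8 events per variable. The figure is arithmetically consistent with 50 events. At the stated 40% STEMI rate the count would be 0.40 × 110 = 44, giving 44/7 = 6.3 to 44/6 = 7.3.

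**2. Places and candidates.** Taking out the three named markers leaves 6 − 3 = 3 or 7 − 3 = 4 places. From 40 transcripts there are C(40,3) = 9,880 or C(40,4) = 91,390 possible sets. Counting candidates instead of entered terms gives 50/(40 + 3) = 1.2 events per candidate.

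**3. What the qPCR gate removes.** On a log2 reading, the planned effect is log2(2.2)/1.4 = 1.14/1.4 = 0.81 SD. With 50 per group and alpha 0.01, power is 0.93 two-sided and 0.96 one-sided, close to the stated 95%. On the plan's own figures, 40 × 0.98 × 0.95 = 37 transcripts would pass, so the gate leaves far more than 3-4. It also uses no fresh outcomes: 20 of the 50 events in each model served discovery, and all 50 serve the gate.

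**4. Consequence of picking the top four, without the gate.** Monte Carlo with Table 2 counts. Assumptions not in the protocol: three clinical markers at 0.6 SD each (0.8 SD in the rows marked *), correlation 0.3 between markers and, except in the rows marked *, between transcripts. The four of 40 transcripts with the largest differences are chosen in the same patients, and AUC is then measured in 2,000 new patients.

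| Group; transcript effect | Clinical alone, new | Selected, apparent | Selected, new | Runs worse than clinical |
|---|---|---|---|---|
| STEMI; none | 0.706 | 0.792 | 0.657 | 100% |
| STEMI; 0.2 SD | 0.705 | 0.806 | 0.695 | 60% |
| STEMI; 0.3 SD | 0.707 | 0.816 | 0.720 | about 19% |
| STEMI; 0.81 SD (planned) | 0.705 | 0.912 | 0.831 | 0% |
| STEMI; 0.77 SD, only through the clinical markers* | 0.770 | 0.837 | 0.728 | 100% |
| NSTEMI; none | 0.708 | 0.770 | 0.670 | 100% |
| NSTEMI; 0.77 SD, only through the clinical markers* | 0.773 | 0.823 | 0.740 | 100% |

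Apparent minus new-patient AUC in the STEMI rows is 0.135, 0.111, 0.096, 0.081 and 0.109. It is positive in every row, including those where the selected model is truly better.

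**5. With the gate and the patient overlap.** Discovery was run in 20 v 20 of the same patients, followed by the p < 0.01 gate:
- No informative transcript: apparent 0.76, new patients 0.59 (gap 0.17).
- Planned effect: apparent 0.93, new patients 0.81 (gap 0.12).
- A score trained in discovery but judged in all patients, no informative transcript: 0.75 against 0.60 (gap 0.15).

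The last line shows that a single score is not enough while the discovery patients stay in the evaluation.

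**6. Room outside discovery.** Table 2 leaves 50 − 20 = 30 events per group, with 60 − 20 = 40 STEMI and 118 − 20 = 98 NSTEMI non-events. One score plus three markers gives 30/4 = 7.5 events per variable, in line with the plan's 7-8. If STEMI yields 44 events, (44 − 20)/4 = 6.0.

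**The case against.** Three stronger readings are tempting, and the documents do not support them.

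- *The model must pick single transcripts.* Nothing says so. The protocol does not state which variables fill the 6/7 places, and it often treats the signature as one entity. A single score would fit. Forty is a planning input for discovery, not a fixed panel size.
- *The 6/7 figure is the only safeguard.* Discovery has an FDR of 0.02, and only transcripts that pass qPCR, planned at alpha 0.01, go forward. In a simulation of the gate without patient overlap (50 v 60, clinical markers at 0.4 SD), none of 40 uninformative transcripts passed in 69% of runs, and the loss was small (0.660 against 0.674 for clinical alone). At 0.3 SD the selected model was better (0.690 against 0.676). This stands as far as it goes, but the protocol's gate does include the discovery patients, and step 5 shows that the inflation then remains.
- *The final model will predict worse than the clinical markers.* At the planned effect, carried independently of those markers, it predicts better in every run.

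Two further objections have some force. Pooling STEMI and NSTEMI (100 v 178) eases the problem: at 0.3 SD even ungated selection gave 0.691 against 0.682 for clinical alone. The 6/7 sentence, however, is written for the two separate models. Score construction and shrinkage are also commonly left to the SAP, which is not shown, so their absence is not the point here. The point is that the protocol makes a positive sizing statement on a count that does not limit the search, and fixes a validation set that contains the discovery patients.

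**Conclusion.** The concern holds in conditional form. If individual transcripts are chosen for the 3-4 remaining places in the same patients, the c-statistic and the added value will be overstated: by about 0.08 to 0.14 AUC in the STEMI scenarios without the gate, and by 0.12 to 0.17 in the two scenarios with the gate and the overlap. Whether the model truly falls below the clinical markers depends on how much the transcripts add. It can if they add little, even when each differs by nearly the planned amount. It does not if they independently carry the 2.2-fold effect at sigma 1.4.

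The marker strengths, correlations and selection rule in the simulations are assumptions, so the sizes are indicative. The direction of the optimism was the same throughout. The 6/7 arithmetic is not wrong; it answers a different question from the one the analysis poses.

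**What to change.** 1. Define the ACS_signature as one prespecified score, with transcripts, directions and weights locked from the discovery data before any qPCR result is linked to outcome. One example is the mean of standardised log2 expression signed by the discovery direction.
2. Enter it as one term beside NT-proBNP, Tn-hs and CK-MB.
3. Estimate its AUC and added value in the patients not used for discovery (30 events per group on Table 2). Alternatively, report optimism-corrected performance with every selection step, including discovery and the qPCR gate, repeated in each resample. Under the first option, fitting four coefficients still leaves some optimism, so a corrected c-statistic should be given there too.
4. Restate the 6/7 sentence to match (four terms, and the events available outside discovery), and label single-transcript models descriptive.

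The cost is wording and one scoring step, with no new patients or assays. If weights are used, their transfer from sequencing to the qPCR scale has to be settled in advance. The price is fewer events in the added-value estimate, a less favourable AUC, and no re-weighting of individual transcripts in the final model. A discovery-trained score will not always out-predict selection. Its advantage is that its performance can be estimated fairly.
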